Once enrolled, both survivors and supporters may choose to opt out of all study questionnaires and still receive the intervention, although they will not be paid for questionnaires. Survivors and supports are permitted to individually withdraw without affecting the eligibility of the other participant (i.e., if a survivor withdraws or cannot be reached, the supporter may still receive the intervention and be paid for questionnaires), but the survivor participant may request to withdraw both themselves and their supporter from the study at any time.

11c. Strategies to improve adherence to intervention protocols, and any procedures for monitoring adherence

All assessments will occur via online self-report surveys. These will be auto-generated from our secure online system, and participants will receive reminders from the clinician within one week of not completing surveys, to remind participants to submit their answers. Survivors and supporters will be paid \$10, \$10, \$20, \$30, and \$40 for baseline, post-session-1, 1-month, 2-month, and 3-month assessments, respectively (total possible per person: \$110). Participants may choose to be paid via preloaded debit card or emailed gift card.

Staff will do weekly checks and audits of all study interactions & documentation to ensure protocol adherence.

11d. Relevant concomitant care and interventions that are permitted or prohibited during the trial

[figure not shown]
Participants will not be restricted from accessing any care or interventions during the course of the trial. It is likely that individuals recruited from the Harborview Abuse and Trauma Center and other key recruitment sites will receive treatment for sexual-assault-related distress while enrolled in the study.

12. Outcomes

See ClinicalTrials.gov

13. Participant timeline

(A schematic diagram is highly recommended)

14. Sample size

Estimated number of participants needed to achieve study objectives

60-72 dyads (120-144 participants)

How sample size was determined

Including clinical and statistical assumptions supporting any sample size calculations

As this is a pilot trial, the sample size was selected primarily for feasibility rather than significance testing.

15. Recruitment

Recruitment sites and procedures; site-specific and general strategies for achieving adequate participant enrollment to reach target sample size

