Reference to where other details of the statistical analysis plan can be found, if not in the protocol

Analyses will be conducted with the intent-to-treat sample. As this study is not powered to detect statistical significance, we will examine the direction and magnitude of effects to preliminarily understand efficacy and test significance in an exploratory manner only. Within-group ds will be calculated as the mean-level difference in scores from baseline to follow-up for each condition divided by the standard deviation of change scores. Between-group ds will represent relative change between conditions and will be calculated as the difference between within-group ds.

Acceptability (H1)

We will use descriptive statistics to summarize acceptability ratings among dyads randomized to dyadic or supporter-only CARE. We will use independent-samples t-tests and between-group *ds* to compare acceptability by condition.

Efficacy (H2–4)

We will calculate within- and between-group *ds* to represent mean changes on focal outcomes. We will use the reliable change index to quantify whether change is unlikely to be attributable to measurement error, and we will report odds ratios for differences in percent with reliable improvement by condition. We will also report the percent of participants meeting diagnostic criteria based on the PCL at baseline and 3-month follow-up.

Paired sample t-tests will evaluate mean changes from baseline to follow-up. We will test time-by-condition interactions in random-effects models using maximum likelihood estimation to account for missing data. We will test covariates including relationship type, study clinician, participant age, and prior assault history. We will conduct sensitivity analyses with English and Spanish-language participants separately.

20b. Methods for any additional analyses

(eg, subgroup and adjusted analyses)

We will test moderation and visually examine results across groups as a function of:

- Baseline PTSD severity and PCL score \geq cutoff of 33
- Relationship type (friend, parent, partner, other)
- Caregiver burden (Impact on Friends - Ineffectiveness Subscale)

We will conduct sensitivity analyses in the following samples:

- English speakers only

20c. Analysis population and missing data

Definition of analysis population related to nonadherence (eg, as randomized analysis), and any statistical methods to handle missing data (eg, multiple imputation)

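### The between-group d is a difference of two within-group ds with no common SD named; with each arm's own SD its size shifts when the SDs differ and it is noisier even when they are equal

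*Combined protocol and SAP*

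**What the plan says.** Section 20a of the combined protocol and SAP defines the within-group d as mean change from baseline "for each condition divided by the standard deviation of change scores". It then builds the comparison from it: "Between-group ds will represent relative change between conditions and will be calculated as the difference between within-group ds". It does not state whether the SD is each arm's own, pooled over the compared arms, or taken from the whole sample, and no other section names a common SD.

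The same section sets the role of these effect sizes: "we will examine the direction and magnitude of effects to preliminarily understand efficacy and test significance in an exploratory manner only". Two other between-arm analyses are planned for H2–H4: "We will test time-by-condition interactions in random-effects models using maximum likelihood estimation to account for missing data", and "we will report odds ratios for differences in percent with reliable improvement by condition". Neither is named as the source of d.

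Section 14 gives 60–72 dyads and explains that "the sample size was selected primarily for feasibility rather than significance testing". Section 8 gives three arms at 1:1:1.

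**The concern.** H3 and H4 (Section 7) are comparisons with waitlist. The between-group d is the only standardised mean comparison between arms that the plan defines, and the plan reads efficacy largely from the size of effects. If each arm is divided by its own SD, the two terms are on different scales. A difference in spread then enters the reported effect as if it were a difference in mean change. Even with equal true SDs, estimating two SDs separately at about 20 per arm adds error, and that error grows with the change common to both arms. Two analysts could follow the text faithfully and report different values from the same data.

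**Working it through.** **No plan figure to reproduce.** The sample size rests on feasibility, and the document gives no SD, expected change, alpha or power.

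**Inputs from the document.** 60/3 = 20 to 72/3 = 24 dyads per arm, before any attrition.

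**Assumed inputs.** Units are waitlist change-score SDs, with improvement positive. Waitlist improves by w = 0, 0.3, 0.5 or 0.8; CARE improves by w + 0.5; r is the CARE/waitlist ratio of change-score SDs. Change scores are normal.

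**Formulas.**
- Own-arm d = M1/S1 − M0/S0 = (w + 0.5)/r − w.
- Pooled d = (M1 − M0)/√((S1² + S0²)/2) = 0.5/√((r² + 1)/2).

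**Step 1: expected size with unequal SDs.** At r = 1.25 the pooled d is 0.5/√1.28125 = 0.44. At r = 0.8 it is 0.5/√0.82 = 0.55.

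| w | Own-arm d, r = 1.25 | Against 0.44 | Own-arm d, r = 0.8 | Against 0.55 |
|---|---|---|---|---|
| 0 | 0.40 | 9% smaller | 0.63 | 13% larger |
| 0.3 | 0.34 | 23% smaller | 0.70 | 27% larger |
| 0.5 | 0.30 | 32% smaller | 0.75 | 36% larger |
| 0.8 | 0.24 | 46% smaller | 0.83 | 49% larger |

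The own-arm index can also be non-zero when mean changes are equal: changes of 10 and 10 with SDs 15 and 10 give 10/15 − 10/10 = −0.33, against 0 pooled.

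**Step 2: precision with equal SDs (r = 1).** With d1 and d0 the true within-group ds, the large-sample variances are 2/n + (d1² + d0²)/(2(n−1)) for own-arm and 2/n + (d1 − d0)²/(4(n−1)) for pooled. The difference is (d1 + d0)²/(4(n−1)), which is never negative and grows with shared change. For d1 = 1.0, d0 = 0.5, n = 20:
- own-arm: 0.100 + 1.25/38 = 0.133, SE 0.365;
- pooled: 0.100 + 0.25/76 = 0.103, SE 0.321;
- variance ratio 1.29.

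At this n the large-sample formula understates the gap. Simulation gives SEs of 0.390 and 0.331, ratio 1.39. Simulated results for r = 1, n = 20:

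| w | Variance ratio, own-arm/pooled | The two ds differ by more than 0.2 |
|---|---|---|
| 0 | 1.10 | 3% of simulated trials |
| 0.3 | 1.24 | 15% |
| 0.5 | 1.39 | 26% |
| 0.8 | 1.71 | 42% |

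The mean estimates are 0.52 own-arm and 0.51 pooled, so there is no material bias. At n = 24 the variance ratios are 1.08/1.22/1.37/1.68.

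**Step 3: wrong sign, n = 20, w = 0/0.3/0.5/0.8.**
- r = 1.25: 10.7/15.6/19.6/26.5% own-arm, 8.1% pooled.
- r = 0.8: 2.8/2.4/2.4/2.6% own-arm, 4.0% pooled.

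The own-arm d does worse when CARE has the larger spread and better when it has the smaller.

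**Step 4: reversal of the expected sign.** This needs S1/S0 > M1/M0: 0.8/0.3 = 2.67, 1.0/0.5 = 2.00 and 1.3/0.8 = 1.625 for w = 0.3, 0.5 and 0.8. It cannot happen at w = 0.

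**The case against.** The case for leaving the text alone has five parts.

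- **The text does not specify own-arm SDs.** True, and a common SD would remove the problem. But the wording attaches the calculation to each condition, so own-arm is the natural reading, and nothing rules it out.
- **The effect may be close to nil.** This stands for outcomes with little spontaneous change. Natural recovery is described only for PTSD symptoms (background section), and the document does not say that disclosure frequency, negative reactions or responsiveness will shift on waitlist. At w = 0 and equal SDs the variance ratio is only 1.10.
- **Pilot noise dominates.** This also stands. With equal SDs, n = 20 and w = 0.3, the pooled d itself misses the true 0.5 by more than 0.2 in 54% of simulated trials, against 57% for own-arm. A better formula will not make the magnitude reliable; it removes avoidable error.
- **Other analyses carry the comparison.** The time-by-condition models and odds ratios are free of this problem and limit the consequence. They do not correct the d that will be reported.
- **A difference of standardised changes is a definable index.** It is, but readers will take a between-group d for a standardised difference in mean change.

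A reader might infer more: that the formula is biased against CARE, or that it will probably point the wrong way. The document supports neither. It gives no reason to expect CARE to have the larger SD, the distortion and the wrong-sign rates run in both directions, and reversal of the expected sign needs marked heterogeneity.

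**Conclusion.** The concern holds in a limited, conditional form. The missing denominator is a fact of the text. The distortion follows only if own-arm SDs are used, and then in proportion to the inequality of the SDs and the change shared by the arms. Over the assumed range, d runs from 9–46% too small (SD ratio 1.25) to 13–49% too large (ratio 0.8) relative to the pooled version. With equal SDs the cost is precision only, a variance ratio of 1.10–1.71 at 20 per arm. The upper ends are most relevant to PTSD symptoms, where natural recovery makes change in every arm plausible; the lower ends apply where waitlist stays flat. All of this rests on assumed means and SDs and on normal change scores, so the actual size cannot be fixed from the document. Severity is minor to moderate.

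The H1 use of between-group ds might be read as a second fault, because Section 7 places acceptability at 1 month and no baseline rating is described, so a change-based d does not fit. The accompanying plan, "We will use independent-samples t-tests", makes an ordinary two-group d the evident meaning. That calls for clarification and adds no weight here.

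**What to change.** In Section 20a, define the between-group d as the mean change in one condition minus the mean change in the comparison condition, divided by the pooled change-score SD of the two arms compared, preferably with a 95% CI. If a common SD was intended all along, naming it is enough. Keep the within-group ds as descriptive summaries and state their denominator. As a clarification, say that the H1 acceptability d is the difference in 1-month mean ratings between dyadic and supporter-only CARE divided by their pooled SD.

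The cost is about two sentences, plus the clarifying one for H1. No new data are needed, and the other planned analyses are unchanged.

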Dyadic CARE involves two telehealth sessions with a clinician, the survivor, and a supporter of the survivor's choice. Session content uses cognitive-behavioral strategies (e.g., encouraging non-avoidance) to encourage communication and improve supporters' responses in trauma-related conversations. Between sessions, both the survivor and the supporter are instructed to review session content and have guided discussions with the assistance of a workbook.

Supporter-Only CARE

Supporter-only CARE involves two telehealth sessions with a clinician and a supporter of the survivor's choice, without the survivor present. Session content uses cognitive-behavioral strategies (e.g., encouraging non-avoidance) to

encourage communication and improve supporters' responses in trauma-related conversations. Between sessions, both the survivor and the supporter are instructed to review session content and have guided discussions with the assistance of a workbook.

Comparison

Waitlist Control

After completing baseline, participants will be invited to schedule a CARE session in 3 months (i.e., after the completion of all study assessments). The version of CARE received at that point will be selected by the survivor.

Participants will complete self-report assessments at post-session-1, Month 1, Month 2, and Month 3.

11b. Criteria for discontinuing or modifying allocated interventions for a given trial participant

Participants who withdraw consent for participation will no longer be contacted by study staff or sent automated reminders to complete study tasks.

Participants will be withdrawn from the research if at any point if it becomes known that a participant does not meet eligibility criteria for the study, if a participant's condition deteriorates, or if it becomes known that they require a higher level or different type of care that is incompatible with study participation. If this occurs, participants will be asked to withdraw from the study and appropriate referrals will be made.

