We will use an intent to treat analysis, in which participants will be retained in the group to which they were originally randomized. Outcome data from all participants will be included in analyses. We will also explore the use of randomization-based efficacy estimators (White, 2005).

Methods: Monitoring

21. Data monitoring

21a. Data monitoring committee

Composition of data monitoring committee (DMC)

N/A

Summary of its role and reporting structure

N/A

Statement of whether it is independent from the sponsor and competing interests

Reference to where further details about its charter can be found, if not in the protocol

N/A

Alternatively, an explanation of why a DMC is not needed

Given that this is a pilot trial of an intervention with minimal risks, we will not retain a data monitoring committee.

21b. Description of any interim analyses and stopping guidelines

Including who will have access to these interim results and make the final decision to terminate the trial

No interim analyses will be conducted.

We will employ the following stopping rule for the clinical trial: if there is clear evidence of harm. Although we do not expect any physical harms or serious psychological harms beyond minimal distress, we have several procedures for monitoring harm from the intervention, including asking participants to contact us if they experience any adverse events, offering additional resources to those with very high levels of mental health symptoms and problem drinking that we identify through data monitoring, and providing resources after baseline and at every follow-up time point. We do not expect there to be overwhelming evidence of the harm of the intervention, but we will monitor this and stop the trial if this is indicated. We also do not expect that there will be no likelihood of demonstrated treatment benefit (futility) for the intervention as compared to control.

22. Harms

Plans for collecting, assessing, reporting, and managing solicited and spontaneously reported adverse events and other unintended effects of trial interventions or trial conduct

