All participants will be fully informed of how to contact the investigators and/or the UW IRB to report complaints or adverse events via explicit instructions in the consent form. The PI and co-I [name] are well-versed in the requirements and procedures for monitoring and reporting adverse events and complaints to the IRB for review. [name] has managed this process as PI of several previous clinical trials and will work closely with Dr.

[name] to provide guidance and consultation in this process. All adverse events will be reviewed by [name] and other members of the treatment team to determine the seriousness of the adverse events. The PI and co-Is have a wealth of experience in managing adverse psychological events both in the context of clinical trials research and clinical practice and are competent to handle any adverse psychological events which may arise. We will follow institutional policies for reporting serious adverse events (SAEs) and adverse events (AEs) to the IRB and OVW. On a daily basis, [name] will be responsible for data and safety monitoring and will provide continuous, close data monitoring. [name] will follow UW's SAE reporting policy in promptly reporting SAEs to the UW Institutional Review Board (IRB) and to OVW. [name] will report all SAEs to the IRBs within 24 hours. A report of all non-serious adverse events will be provided to the IRB yearly. The PI and co-Is will meet twice a year regarding safety and monitoring procedures. This meeting will be used to review any problems in implementing procedures. [name] will also monitor safety data as part of the yearly review. Safety evaluations will include AEs and longitudinal symptom measures. Safety evaluations will also consider factors external to the study, such as scientific or therapeutic developments that may have an impact on the safety of the participants or the ethics of the study.

23. Auditing

Frequency and procedures for auditing trial conduct, if any, and whether the process will be independent from investigators and the sponsor

No auditing will be conducted.

Ethics and Dissemination

24. Research ethics approval

Plans for seeking research ethics committee/institutional review board (REC/IRB) approval

We have obtained ethical approval from the University of Washington IRB.

25. Protocol amendments

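### Section 20a reports reliable improvement by condition but no by-arm count of reliable worsening, and withdrawal for deterioration under 11b could remove some of the people who worsen

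*Combined protocol and SAP*

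**What the plan says.** All references are to the combined protocol and SAP.

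- **20a, Efficacy (H2–4).** The index is introduced without a direction: "We will use the reliable change index to quantify whether change is unlikely to be attributable to measurement error". The comparison between conditions then covers one direction: "we will report odds ratios for differences in percent with reliable improvement by condition". The other categorical result is a PCL percentage: "We will also report the percent of participants meeting diagnostic criteria based on the PCL at baseline and 3-month follow-up". It is not stated to be by condition. The remaining summaries are means: within- and between-group ds, paired t-tests and time-by-condition interactions.
- **20b.** "We will test moderation and visually examine results across groups as a function of" baseline PTSD, relationship type and caregiver burden.
- **21b and 22.** There is a stopping rule for harm. Adverse events are captured partly by "asking participants to contact us if they experience any adverse events". Section 22 adds: "Safety evaluations will include AEs and longitudinal symptom measures". Neither section defines worsening on a scale or commits to a summary by arm.
- **11a, Waitlist Control.** Waitlist dyads answer the surveys too: "Participants will complete self-report assessments at post-session-1, Month 1, Month 2, and Month 3". Their own CARE comes later: "participants will be invited to schedule a CARE session in 3 months (i.e., after the completion of all study assessments".
- **11b.** Participants are to be withdrawn if they deteriorate, or if they turn out to need a higher level or different type of care that cannot be combined with the study.

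**The concern.** CARE encourages trauma-related conversations between recently assaulted survivors with elevated PTSD symptoms and a supporter. The background section itself notes that negative reactions to disclosure raise the risk of psychopathology. A conversation that goes badly is therefore a plausible way for an individual dyad to be set back, even if CARE helps on average. Some people will also worsen without CARE, so a count of worsening means something only beside the waitlist count.

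The trial can make that comparison, because all arms complete self-report surveys on the same schedule and the index is already planned. Followed as written, however, the plan commits to only the favourable direction of that index by arm. With no interim analysis and no data monitoring committee, the final report is the main place where a reader could see the other direction. What is at stake is how much the pilot can say about individual harm when a larger trial is considered.

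**Working it through.** The plan gives no worsening rate, no reliable-change cut-off and no power figure, so there is no stated figure to reproduce. Scores, rates and withdrawals below are assumptions.

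**1. What each planned summary can show**

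| Summary | Shows | Does not show |
|---|---|---|
| Reliable-improvement odds ratio (20a) | Who got better, by arm | Whether the rest were unchanged or worse |
| Between-group ds, time-by-condition models (20a) | Average worsening by arm | How many people worsened |
| PCL diagnostic percent (20a) | Change in the share of survivors meeting criteria | Worsening in survivors already meeting them; supporters; by-arm split not stated |
| Moderation (20b) | Worsening linked to the named factors | Worsening unrelated to them |
| Safety evaluations (22) | Internal review of symptoms | A stated threshold or by-arm summary |

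**2. Per-arm size.** 60/3 = 20 and 72/3 = 24 dyads (section 14; 1:1:1 allocation).

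**3. Same planned comparison, different worsening.** Change scores, positive = improvement, 20 per arm. Within-group d = mean change / SD of change; between-group d = CARE d − waitlist d (20a). The reliable-change cut-off is assumed to lie above 5 and at most 15 points.

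- Waitlist: 8 at +20, 11 at 0, 1 at −20. Mean = (160 − 20)/20 = 7.0.
- CARE case B: 8 at +20, 7 at 0, 5 at −20. Mean = (160 − 100)/20 = 3.0.
- CARE case C: 8 at +15, 8 at −5, 3 at 0, 1 at −20. Mean = (120 − 40 − 20)/20 = 3.0.

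| | Mean | SD | d | Mean contrast | Between-group d | Improved | Worsened |
|---|---|---|---|---|---|---|---|
| Waitlist | 7.0 | 11.74 | 0.596 | – | – | 8/20 | 1/20 |
| B | 3.0 | 16.25 | 0.185 | −4.0 | −0.41 | 8/20 | 5/20 |
| C | 3.0 | 10.81 | 0.278 | −4.0 | −0.32 | 8/20 | 1/20 |

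Both cases give an improvement odds ratio of 1.0 and a mean contrast of −4.0. The planned summaries show a deficit in both. They do not tell the reader that five people worsened in B and one in C; the larger SD in B is only an indirect hint.

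**4. Precision of the missing comparison.** Wilson limits for each proportion: (p + z²/2n ± z√(p(1−p)/n + z²/4n²)) / (1 + z²/n). Newcombe limits for the difference D = p₁ − p₂: lower = D − √((p₁−l₁)² + (u₂−p₂)²); upper = D + √((u₁−p₁)² + (p₂−l₂)²).

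- 5/20 has Wilson limits 0.112 to 0.469; 1/20 has 0.009 to 0.236.
- Lower = 0.20 − √(0.138² + 0.186²) = −0.032. Upper = 0.20 + √(0.219² + 0.041²) = 0.423.
- Result: +20 points (95% CI −3 to +42).

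At equal true rates, evaluated at expected counts, one CARE version vs waitlist:

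| Assumed rate | 20 per arm | 24 per arm | 16 per arm (80% of 20) | 19 per arm (80% of 24) |
|---|---|---|---|---|
| 10% | ±21 | ±19 | ±24 | ±22 |
| 20% | ±25 | ±23 | ±27 | ±25 |

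With no events in either arm, the upper limit is still 16 points (20 per arm) or 14 points (24 per arm).

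**5. Effect of 11b.** Take case B and suppose 3 of the 5 CARE worseners are withdrawn before follow-up, with none withdrawn on waitlist.

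- Worsening among those with data: 2/17 vs 1/20, 11.8% − 5.0% = +7 points (95% CI −14 to +30), instead of +20.
- Improvement among those with data: 8/17 vs 8/20, odds ratio (8/9)/(8/12) = 1.33, instead of 1.0.
- Counting the 3 withdrawals as worsened: (2 + 3)/20 = 5/20 vs 1/20, which restores +20 points.

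A worsening table limited to people with scores can therefore understate the difference in just the situation it is meant to reveal.

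**The case against.** The strongest reply is that most of this is already covered. The plan examines the direction of effects, computes signed ds, fits time-by-condition models, plots moderators, reviews symptom measures for safety and can stop for harm. Even in a case built so that the means cancel (8 CARE participants at +30, 7 at 0, 5 at −20: mean 140/20 = 7.0, SD 20.80, d 0.337), the planned between-group d is 0.337 − 0.596 = −0.26, because it divides by the SD of change. The pilot is sized for feasibility, and the added intervals would rarely change a conclusion. Nothing forbids reporting worsening later. All of this stands, and it limits the point to a count of individuals.

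It does not remove the gap. A negative d does not separate fewer or smaller gains from people getting worse, as cases B and C show. Low precision applies equally to the improvement odds ratios, which the plan reports anyway. Stating the count in advance takes away discretion over whether an unfavourable result appears.

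A further objection is that follow-up scores are themselves open to loss through 11b. That is correct, and it is why withdrawals belong beside the count. The loss is not certain: 18b says staff will try to reach participants for all follow-ups unless told otherwise, and 20c includes outcome data from all participants. The maximum likelihood models would also use waves completed before withdrawal; a change score at one follow-up would not.

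A reader might infer that harm under CARE would go unmonitored, or that the plan is built to hide it. The documents support neither: 21b and 22 provide for monitoring, and 20a does not confine the index to improvement.

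**Conclusion.** The point holds as a minor gap in reporting. Section 20a commits to a by-condition result for reliable improvement only, and no section states how many people reliably worsened in each arm. The omission biases no planned estimate and leaves the 21b stopping rule and section 22 monitoring unchanged.

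Its size depends on assumed figures. In the example, a difference of 5/20 vs 1/20 is invisible in the improvement odds ratio and cannot be read off the mean contrast. Three withdrawals under 11b would shrink that difference from +20 to +7 points among those with data. The scores, the cut-off range, the 10 to 20% rates, the 80% completion and the three withdrawals are all illustrative. The per-arm sizes come from the plan.

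Two stronger readings should be avoided. Nothing in the documents indicates that CARE makes people worse, or how often. Nor would the added table settle the question: at this size it could exclude only large harms.

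**What to change.** In 20a, directly after the reliable-improvement odds ratios, add wording to this effect:

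> For survivor PTSD, survivor stress and supporter stress, we will report by randomised arm the number and percent with reliable worsening, using the same index in the opposite direction at the same follow-up, and the number with data. For each CARE version against waitlist we will give a risk difference with a Newcombe 95% CI, for description only. Beside this we will report by arm the number withdrawn under 11b for deterioration or need for a higher level of care, and will repeat the comparison counting those withdrawals as worsened.

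The cost is a few sentences, three table rows (3 measures × 2 contrasts = 6 intervals), the withdrawal counts and one repeat of the six intervals. No visits, questionnaires or participants are added. The reason for each 11b withdrawal must be recorded by arm. Relationship quality, also an H4 outcome, is left out to keep the table to symptom-type measures; the sponsor could add it.

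The downside is over-reading. The table should state that the intervals are wide and that one including zero is not evidence of no harm. The repeat analysis has its own limit: clinicians see CARE participants in sessions, so deterioration may be noticed more readily there than on waitlist. The two versions should therefore be read together.
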